4.5.5 Laboratory, Biomarker, and Other Biological Samples

Samples for the following laboratory tests will be sent to The Doctors Laboratory for analysis:

- Hematology: WBC count, RBC count, hemoglobin, hematocrit, platelet count, and differential count (neutrophils, eosinophils, basophils, monocytes, lymphocytes, other cells)
- Chemistry panel (serum): sodium, potassium, chloride, glucose, BUN or urea, creatinine, total protein, albumin, phosphate, calcium, total and direct bilirubin, alkaline phosphatase, ALT, AST, urate, and LDH
- Coagulation: INR, aPTT, and PT
- Virology: HIV, hepatitis B surface antigen (HBsAg), Anti-HCV at screening
- Follicle Stimulating Hormone (FSH; post-menopausal female subjects only)
- Pregnancy test

All women will have a serum pregnancy test at screening and a urine pregnancy test on Day -1 of each period.

- Urinalysis (pH, specific gravity, glucose, protein, ketones, blood) and urine drug screen samples will be analyzed by dipstick at the clinic. The urine drug screen will test for the following: amphetamines, barbiturates, benzodiazepines, cocaine, marijuana/cannabis, methadone, methamphetamine/ecstasy, morphine/opiates, phencyclidine, and tricyclic anti-depressants. Microscopic urinalysis examination, if required (sediment, RBCs, WBCs, casts, crystals, epithelial cells, bacteria)

Entrectinib—Genentech, Inc.
35/Protocol GP41341, Version 1 – 02 April 2019

Scheduled blood samples for safety laboratory tests will be taken following an 8-hour fast. The acceptable deviation from the nominal post-dose time point (96 hours) is ± 2 hours.

Alcohol breath tests and carbon monoxide breath tests will be performed at the clinic. A positive alcohol breath test will exclude that subject from dosing during that admission. A carbon monoxide result of greater than 10 ppm will exclude the subject from the study.

Samples for the following laboratory tests will be sent to [REDACTED] for analysis:

- Plasma samples for pharmacokinetic analysis

For sampling procedures, storage conditions, and shipment instructions, see the Clinical Sample Processing Manual.

The total blood volume for each subject will not exceed 550 mL in a 4-week period. The first 0.5 mL of blood withdrawn via cannula will be discarded.

Residual pharmacokinetic samples will be destroyed no later than 5 years after the final Clinical Study Report has been completed.

When a subject withdraws from the study, samples collected prior to the date of withdrawal may still be analyzed, unless the subject specifically requests that the samples be destroyed or local laws require destruction of the samples. However, if samples have been tested prior to withdrawal, results from those tests will remain as part of the overall research data.

Data arising from sample analysis will be subject to the confidentiality standards described in Section 8.4.

4.5.6 Electrocardiograms

Single ECG recordings will be obtained at specified time points, as outlined in the schedule of activities (see [Appendix 1](#)). The acceptable deviations from the nominal ECG measurement time points are:

- The pre-dose ECG measurements will be taken ≤ 2 hours before dosing
- Post-dose ECG measurements will be taken ± 15 minutes from the nominal post-dose time point
- Discharge ECG measurements will be taken ± 1 hour from the nominal time point.
- For return visits ECG measurements will be taken ± 4 hours from the nominal return visit time point.

ECGs acquired on different days should be as closely time-matched as feasible. ECG recordings may be obtained at unscheduled time points as indicated. The Day 1, pre-dose assessment in each period will be used as baseline.

Entrectinib—Genentech, Inc.
36/Protocol GP41341, Version 1 – 02 April 2019

All ECG recordings must be performed using a standard high-quality, high-fidelity digital electrocardiograph machine equipped with computer-based interval measurements. Lead placement should be as consistent as possible. ECG recordings must be performed after the subject has been resting in a supine position for at least 5 minutes. All ECGs are to be obtained prior to other procedures scheduled at that same time (e.g., vital sign measurements, blood draws) and should not be obtained within 3 hours after any meal, whenever feasible. Circumstances that may induce changes in heart rate, including environmental distractions (e.g., television, radio, conversation), should be avoided during the pre-ECG resting period and during ECG recording.

For safety monitoring purposes, the investigator must review, sign, and date all ECG tracings. Paper copies of ECG tracings will be kept as part of the subject's permanent study file at the site. The following should be recorded in the appropriate eCRF: heart rate, RR interval, QRS interval, PR duration, uncorrected QT interval, and QTcF based on the machine readings of the individual ECG tracings. Any morphologic waveform changes or other ECG abnormalities must be documented on the eCRF. If considered appropriate by the Sponsor, ECGs may be analyzed retrospectively at a central laboratory.

If at a particular post dose time point the mean QTcF is >500 ms and/or 60 ms longer than the baseline value, another ECG must be recorded, ideally within the next 5 minutes, and ECG monitoring should continue until QTcF has stabilized on two successive ECGs. The Medical Monitor should be notified. Standard-of-care treatment may be instituted per the discretion of the investigator. If a pharmacokinetic sample is not scheduled for that time point, an unscheduled pharmacokinetic sample should be obtained. A decision on study drug discontinuation should be made, as described in Section 4.6.1. The investigator should also evaluate the subject for potential concurrent risk factors (e.g., electrolyte abnormalities, co-medications known to prolong the QT interval, severe bradycardia).

4.5.7 Palatability Questionnaire

Subjects will be asked to complete the palatability questionnaire presented in [Appendix 3](#) at the times indicated in the schedule of activities ([Appendix 1](#)).

4.6 TREATMENT, SUBJECT, STUDY, AND SITE DISCONTINUATION

4.6.1 Stopping Criteria

The study will be halted, and the risk to other subjects evaluated if any of the following criteria are met:

- A serious adverse reaction (i.e., a serious adverse event considered at least possibly related to the IMP administration) in one subject.
- Severe non-serious adverse reactions (i.e., severe non-serious adverse events considered at least possibly related to the IMP administration) in two subjects in the

Entrectinib—Genentech, Inc.
37/Protocol GP41341, Version 1 – 02 April 2019

same cohort of the study, independent of within or not within the same system organ class.

Relatedness will be determined by the investigator.

If the study is halted, a temporary halt will be submitted to the Medicines and Healthcare products Regulatory Agency (MHRA) and ethics committee (EC) in the form of a substantial amendment. The study may be resumed or terminated; however, it will not be resumed until a further substantial amendment to resume the study is submitted and approved by MHRA and EC.

In addition, subjects must permanently discontinue study treatment if they experience any of the following:

- Any medical condition that the investigator or Sponsor determines may jeopardize the subject's safety if he or she continues to receive study treatment
- Investigator or Sponsor determination that treatment discontinuation is in the best interest of the subject
- Pregnancy
- Concurrent illness or requirement for prohibited medication
- Experiencing a serious or severe adverse event including but not limited to:
 - corrected QT interval by Fridericia's formula (QTcF) interval of >500 msec or increase in QTcF interval of >60 msec from baseline (confirmed following a repeat ECG)
 - ALT concentration >3 × the upper limit of the reference range

The primary reason for study treatment discontinuation should be documented on the appropriate eCRF.

For a subject who withdraws because of an IMP-related adverse event, every effort will be made to ensure the subject completes follow-up procedures. Any subject withdrawn or discontinuing the study prematurely because of an IMP-related adverse event or termination of the study will be considered to have completed the study, and will not be replaced. Subjects who discontinue study treatment may be replaced at the discretion of the Sponsor and the investigator to ensure a minimum of 12 evaluable subjects in each study part.

A subject is considered evaluable if they have sufficient data to ensure the primary objective of the relevant study part is met.

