4. MATERIALS AND METHODS

4.1 SUBJECTS

Approximately 31 (15 in Part 1 and 16 in Part 2) healthy male and female volunteers will be enrolled at one investigative site located in the UK.

Up to 4 replacement subjects per study part are permitted in this study to ensure sufficient evaluable subjects; a maximum of 19 subjects in Part 1 and 20 subjects in Part 2 may be dosed in each study part.

Quotient Sciences (the Clinical Research Unit) must have a full medical history from each subject's general practitioner within the last 12 months, prior to enrollment in the study.

Before subjects are admitted to the clinic, The Over Volunteering Prevention System (TOPS) will be checked to ensure that each subject has not participated in a study at another site within at least 3 months of the dosing date.

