4.6.2 Subject Discontinuation from the Study

Subjects have the right to voluntarily withdraw from the study at any time for any reason. In addition, the investigator has the right to withdraw a subject from the study at any time.

Entrectinib—Genentech, Inc.
38/Protocol GP41341, Version 1 – 02 April 2019

Reasons for subject discontinuation from the study may include, but are not limited to, the following:

- Subject withdrawal of consent
- Study termination or site closure
- Adverse event
- Loss to follow-up
- Subject non-compliance, defined as failure to comply with protocol requirements as determined by the investigator or Sponsor

Every effort should be made to obtain a reason for subject discontinuation from the study. The primary reason for discontinuation from the study should be documented on the appropriate eCRF. If a subject requests to be withdrawn from the study, this request must be documented in the source documents and signed by the investigator.

For a subject who withdraws because of an IMP-related adverse event, every effort will be made to ensure the subject completes follow-up procedures. Any subject withdrawn or discontinuing the study prematurely because of an IMP-related adverse event or termination of the study will be considered to have completed the study, and will not be replaced. Subjects who discontinue study treatment may be replaced at the discretion of the Sponsor and the investigator to ensure a minimum of 12 evaluable subjects in each study part.

A subject is considered evaluable if they have sufficient data to ensure the primary objective of the relevant study part is met.

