6.2 SUMMARIES OF CONDUCT OF STUDY

The number of subjects who enroll, discontinue, or complete the study will be summarized. Reasons for premature study discontinuation will be listed and summarized. Enrollment and major protocol deviations will be listed and evaluated for their potential effects on the interpretation of study results.

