7.2 Subject Disposition and Withdrawals

The number and percentage of subjects randomized, dosed, completed and discontinued will be presented by treatment sequence and overall. If any subjects discontinued from the study early, then the number of subjects for each reason for discontinuation will be presented by treatment sequence and overall. However, if none of the subjects discontinued from the study early, then the reasons for discontinuation will not be populated in the summary table.

Subject disposition and withdrawal data will be listed, including details of informed consent.

Protocol deviations and any violations of the inclusion/exclusion criteria will also be listed.

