10.1 Extent of Exposure and Treatment Compliance

The number and percentage of subjects dosed with IMP will be presented for each treatment.

Dosing details (including the date and time of all doses administered and any comments) will be listed. Any recorded deviations from the planned dosing treatment will be listed as protocol deviations.

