10.3.1.1 Overall Summary of Adverse Events

The following will be summarized by treatment:

- number and percentage of subjects reporting at least 1 TEAE
- number and percentage of subjects reporting at least 1 severe TEAE
- number and percentage of subjects reporting at least 1 life-threatening TEAE
- number and percentage of subjects reporting at least 1 IMP-related TEAE
- number and percentage of subjects reporting at least 1 AE of special interest
- number and percentage of subjects reporting at least 1 serious TEAE
- number and percentage of subjects reporting at least 1 TEAE leading to death
- total number of TEAEs
- total number of severe TEAEs
- total number of life-threatening TEAEs
- total number of IMP-related TEAEs
- total number of AEs of special interest
- total number of serious TEAEs
- total number of TEAEs leading to death

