16.2.9.1.4	Palatability Evaluations Individual Values: All Randomized Subjects <Palatability Question> Part 1

Listing Number	Listing Title
16.2.9.2.1.1	Vital Signs Individual Values: All Randomized Subjects Part 2
16.2.9.2.1.2	Vital Signs Individual Values Outside the Reference Range: All Randomized Subjects Part 2
16.2.9.2.2.1	ECGs Individual Values: All Randomized Subjects Part 2
16.2.9.2.2.2	ECGs Individual Values Outside the Reference Range: All Randomized Subjects Part 2
16.2.9.2.3	Physical Examinations Individual Values: All Randomized Subjects Part 2

21 Mock Tables

Genentech, Inc.
Protocol: GP41341

Page x of y

TABLE 14.1.1.1
Subject Disposition by Reason
Summary Statistics: All Randomized Subjects
Part 1

	Treatment Sequence			
	T1T2R (N=XX)	T2RT1 (N=XX)	RT1T2 (N=XX)	OVERALL (N=XX)
	n (%)	n (%)	n (%)	n (%)
Subjects randomized	xx (xx.x)	xx (xx.x)	xx (xx.x)	xx (xx.x)
Subjects dosed	xx (xx.x)	xx (xx.x)	xx (xx.x)	xx (xx.x)
Subjects completed	xx (xx.x)	xx (xx.x)	xx (xx.x)	xx (xx.x)
Subjects discontinued	xx (xx.x)	xx (xx.x)	xx (xx.x)	xx (xx.x)
Reason for discontinuation	xx (xx.x)	xx (xx.x)	xx (xx.x)	xx (xx.x)
REASON 1	xx (xx.x)	xx (xx.x)	xx (xx.x)	xx (xx.x)
...
<All categories on eCRF>	xx (xx.x)	xx (xx.x)	xx (xx.x)	xx (xx.x)

Note: The data in this table are presented in listing xx
T1: 600 mg entrectinib film-coated mini-tablets fed, T2: 600 mg entrectinib film-coated mini-tablets fed, R: 600 mg entrectinib (RXDX-101) F06 hard capsules fed.
A randomized subject is defined as a subject who signed the informed consent, qualified per the inclusion/exclusion criteria and was randomized to a treatment sequence (i.e., allocated a subject number).
A subject may be discontinued for one reason only.

PROGRAM PATH: X:\~\QSC201525\~\TFLS\PRODUCTION\TAB_XX DDMMYYYY HH:MM

(Programming note: This table will be continued for all reasons for discontinuation as recorded on the eCRF. If none of the subjects discontinued from the study early, then reasons for discontinuation will not be populated in the summary table. All percentages are based on the number of subjects who were randomized.)
(Programming note: A similar table will be produced for Part 2 Subject Disposition by Reason, i.e., Table [14.1.2.1]. Treatment sequences will be TR and RT and footnote will state: T: 200 mg F06 HPMC capsules fasted, R: 200 mg entrectinib (RXDX-101) F06 hard capsules fasted.)

Genentech, Inc.
Protocol: GP41341

Page x of y

TABLE 14.1.1.2.1
Analysis Populations

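### Does treating subjects withdrawn for a drug-related adverse event as completers hide those withdrawals in the report?

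*Protocol*

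**What the plan says.** Protocol 4.6.1 (Stopping Criteria) and, in identical words, 4.6.2 (Subject Discontinuation from the Study) state that any subject who leaves early "because of an IMP-related adverse event or termination of the study will be considered to have completed the study, and will not be replaced". The next sentence lets the sponsor and investigator replace other subjects to keep at least 12 evaluable in each part. The one after it says what evaluable means.

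Protocol 4.6.2 also names adverse events and study termination among the grounds for leaving, and requires: "The primary reason for discontinuation from the study should be documented on the appropriate eCRF". Protocol 6.2, the section on reporting study conduct, makes no exception for drug-related cases: "Reasons for premature study discontinuation will be listed and summarized".

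SAP 7.2 says: "The number and percentage of subjects randomized, dosed, completed and discontinued will be presented by treatment sequence and overall". Reason rows are filled if anyone left early and stay blank only if nobody did. Neither SAP 7.2 nor the definitions in SAP 3.2.1 say what completed means. For mock Table 14.1.1.1 (SAP section 21) the programming note reads: "All percentages are based on the number of subjects who were randomized".

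On adverse events, SAP 10.3.1.1 has seven subject counts and seven matching event counts. The nearest to the point is "number and percentage of subjects reporting at least 1 TEAE leading to death". None concerns events that led a subject to stop.

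**The concern.** One subject can fit two categories that the disposition table shows as separate rows. A subject withdrawn for a drug-related event has completed under the only completion rule in the protocol, yet has also discontinued with a reason that the protocol wants summarized. If a programmer followed the first sentence literally, Tables 14.1.1.1 and 14.1.2.1 could show full completion in a study where the drug had made people stop.

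Safety and tolerability is the secondary objective, so this would matter to a reader. Other tables do not fill the gap by themselves. SAP 10.1 promises "The number and percentage of subjects dosed with IMP will be presented for each treatment", but that count falls for a missed dose of any cause. The table of drug-related events does not show who stopped.

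**Working it through.** The plan states no figure on this point, so the check compares the texts, sizes the ambiguity, and then asks which outputs depend on it.

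**Step 1: the two readings against the text.**

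| Text | Completion rule governs reporting | Rule concerns replacement only |
|---|---|---|
| Protocol 4.6.1 and 4.6.2, the rule | Fits the first half of the sentence | Fits the second half and the two sentences that follow |
| Protocol 4.6.2, reason on the eCRF | Reason collected, then not used in the table | Reason collected and used |
| Protocol 6.2, reasons summarized | Needs an exception that is not there | Fits as written |
| SAP 7.2, reasons shown if anyone left early | Needs someone who left early not to count as having left early | Fits as written |

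The rule's own subject is a person withdrawn or stopping before the end. That is the condition on which SAP 7.2 prints reasons, whatever completion label the person also carries. Mock Table 14.1.1.1 prints every reason category on the eCRF. SAP 3.2.1 handles the neighbouring term, evaluable, in the same spirit: it serves decisions on replacement during the clinical phase and is set aside for reporting. That sentence does not mention completion, but it shows how the authors separate the two uses.

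**Step 2: size of the label question.** Let k be the number of subjects withdrawn for a drug-related event and N the number randomized. The completion rate differs between the readings by 100 × k/N percentage points.

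- Planned enrolment (Protocol 6.1), k = 1: 1/15 = 6.7 points in Part 1; 1/16 = 6.3 points in Part 2.
- All four replacements used for other drop-outs. Protocol 4.1 allows that "a maximum of 19 subjects in Part 1 and 20 subjects in Part 2 may be dosed in each study part". Then 1/19 = 5.3 and 1/20 = 5.0 points.
- Sequence columns at planned size (Protocol 4.2): 1/5 = 20.0 points in Part 1; 1/8 = 12.5 points in Part 2.

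The documents give no expected withdrawal rate, so k is an assumption. With k from 1 to 4 and no other drop-outs, completion is 100.0% on the literal reading. On the other reading it is 93.3%, 86.7%, 80.0% and 73.3% in Part 1 (14, 13, 12 and 11 of 15), and 93.8%, 87.5%, 81.3% and 75.0% in Part 2 (15, 14, 13 and 12 of 16). With k = 0 the readings agree.

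**Step 3: what uses the label.**

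- Pharmacokinetic population (SAP 6.2): set by dosing and by the quality of each profile, not by completion.
- Mixed model (SAP 9.2.4): treatment, period, sequence and subject only.
- Safety population (SAP 6.1): at least one dose.
- Adverse event incidence and severity (SAP 10.3.1): all treatment-emergent events, by treatment.

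Only the disposition tables and the completion listing carry the label.

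**Step 4: the missing adverse event row.** The secondary endpoints (Protocol 2.2, SAP 4.2.2) are incidence and severity of adverse events and incidence of abnormalities in the safety assessments. Stopping because of an event is not among them, and no protocol section promises such a table. A row counting all treatment-emergent events that led to stopping would have no split by relatedness, so it would not give the drug-related count at issue. The mock adverse event listing, which also serves as the template for treatment-emergent events, shows period, treatment, relationship and action taken on each line. With 15 or 16 planned subjects per part, the cases can be counted from it by hand.

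**The case for a change.** The strongest case for a change is that the rule joins two statements, completed and not replaced. If only replacement were meant, the first half would be redundant. SAP 3.2.1 shows that the authors knew how to confine a term to the clinical phase, and they did not do so here. Mock Listing 16.2.1.1 has a single yes/no completion flag and shows a withdrawal reason only beside a no, so a literal programmer could lose the reason there too. Even on the favourable reading, disposition is given by sequence. Every Part 1 sequence contains all three formulations, so an adverse event row cannot say which formulation was involved. Settling the definition before database lock would also avoid choosing it with the withdrawals in view.

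Part of this stands. The label is undefined, the first half of the sentence is loosely drafted, and no table ties an event to stopping by formulation. It does not carry the conclusion. Losing the reason altogether would mean departing from Protocol 6.2 and from the trigger in SAP 7.2. SAP section 16 calls the mock outputs illustrative, so they do not override the text. The formulation in play can be read from the adverse event listing.

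**Conclusion.** No change is needed. This is a missing reporting detail that analysts can settle from the surrounding text: those who left early are shown as discontinued with their eCRF reason, and the completion wording is used to decide on replacement. Following the plan as written still reports the reason.

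What remains is one label in Tables 14.1.1.1 and 14.1.2.1 and the matching listing, worth 6.7 or 6.3 percentage points of overall completion per affected subject at planned size. The larger by-sequence figures reflect only columns of 5 or 8 subjects, and tolerability is summarized by treatment. The geometric mean ratios, their 90% intervals, and the incidence and severity of adverse events are the same on either reading. A count of events leading to stopping would be an optional convenience, not the repair of an omission.

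The conclusion assumes that the eCRF carries adverse event as a reason, as Protocol 4.6.2 implies, and that the listings are produced with the relationship and action fields shown in the mock-ups.

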6.1 DETERMINATION OF SAMPLE SIZE

It is planned that total of 15 subjects will be enrolled in Part 1 and 16 subjects will be enrolled in Part 2 of the study to achieve 12 evaluable subjects in each part. Subjects who withdraw from the study may be replaced at the discretion of the Sponsor and investigator to ensure that in each part 12 subjects complete the study and have evaluable pharmacokinetic data from all treatment periods.

The sample size has been chosen to ensure that the ratios of the geometric means for the pharmacokinetic parameters of entrectinib can be estimated with sufficient precision. In a previous study (Study RXDX-101-15) the within-subject coefficients of variation for $AUC_{0-\infty}$ and C_{max} following administration of a single dose of entrectinib were estimated to be 20% and 16%, respectively. Based on a coefficient of variation of 20%, with 12 evaluable subjects it is estimated that the lower and upper bounds of the 90% CIs of the ratio will be within 1.25x of the corresponding point estimates for each of the two entrectinib pharmacokinetic parameters ($AUC_{0-\infty}$ and C_{max}).

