3.2 Definitions

3.2.1 Subjects Definitions

During the clinical phase of the study, a subject is considered evaluable if they have sufficient data to ensure the primary objective of the relevant study part is met. This will be monitored during the clinical phase to identify any requirement for replacement subjects. This definition will not be used during the reporting phase, including the identification of analysis populations and datasets.

A randomized subject is defined as a subject who signed the informed consent, qualified per the inclusion/exclusion criteria and was randomized to a treatment sequence (i.e., was allocated a subject number).

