5.2 Study Sample Size

It is planned that a total of 15 subjects will be enrolled in Part 1 and 16 subjects will be enrolled in Part 2 of the study to achieve 12 evaluable subjects in each part. Subjects who withdraw from the study may be replaced at the discretion of the Sponsor and principal investigator (PI) to ensure that in each part, 12 subjects complete the study and have evaluable PK data from all treatment periods.

The sample size has been chosen to ensure that the ratios of the geometric means for the PK parameters of entrectinib can be estimated with sufficient precision. In a previous study (Study RXDX-101-15), the within-subject coefficients of variation for $AUC_{0-\infty}$ and C_{max} following administration of a single dose of entrectinib were estimated

to be 20% and 16%, respectively. Based on a coefficient of variation of 20%, with 12 evaluable subjects it is estimated that the lower and upper bounds of the 90% CIs of the ratio will be within 1.25x of the corresponding point estimates for each of the two entrectinib PK parameters ($AUC_{0-\infty}$ and C_{max}).

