9.2 Pharmacokinetic Parameter Reporting Specifications

The following parameters will be reported for each study part as applicable, according to the rounding specifications provided in [Table 4](#):

Study Parts 1 and 2:

t_{max} , C_{max} , AUC_{0-t} , AUC_{0-inf} , %AUCextrap, $t_{1/2}$, λ_z , λ_z Lower, λ_z Upper, CL/F, V_z/F , MPR (based on AUC_{0-inf}) and Frel (based on AUC_{0-t} and AUC_{0-inf}).

The following flags/footnotes may be applied to the PK parameters:

Flag	Footnote
a	Rsq of regression was <0.9
b	Period used for regression analysis was less than 2-fold the calculated half-life
c	Extrapolated portion of AUC_{0-inf} >20%

d	Insufficient post- C_{max} data points for estimation of λ_z
e	Entire profile BLQ, no PK parameters could be calculated
f	Quantifiable pre-dose values were observed, however were considered less than 5% of C_{max}

In the event that the R-squared (Rsq) of regression was <0.9 ("a" flag) or the extrapolated portion of $AUC_{0-\infty}$ >20% ("c" flag), then the parameter estimates derived using λ_z and/or $AUC_{0-\infty}$ will be deemed unreliable and will be listed but excluded from the summary statistics and formal statistical analysis.

In the event that the period used for regression analysis was less than 2-fold the calculated half-life ("b" flag) parameter estimates derived using λ_z will be listed, flagged and included in summary statistics and formal statistical analysis.

In the event that quantifiable pre-dose values less than 5% of C_{max} were observed ("f" flag), all parameter estimates for the profiles affected will be listed, flagged and included in summary statistics and formal statistical analysis.

In the event that quantifiable pre-dose concentrations greater than 5% of C_{max} are observed, requirements for further action will be agreed with Genentech and documented at the same time as the PK population.

Additional flags may be applied based on emerging data.

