9.2.4 Statistical Analysis of Pharmacokinetic Parameters

Formal statistical analysis will be performed on the entrectinib and M5 PK parameters C_{max} , AUC_{0-t} and AUC_{0-inf} to assess the relative bioavailability between test and reference formulations. The PK parameters will undergo a natural logarithmic transformation and will be analysed using mixed effect modelling techniques. The model will include terms for treatment, period and sequence fitted as fixed effects and subject nested within sequence fitted as a random effect.

The following pairwise treatment comparisons (*test versus reference*) are of interest in Part 1:

- 600 mg F15 vs 600 mg F06
- 600 mg F16 vs 600 mg F06

The following pairwise treatment comparison (*test versus reference*) is of interest in Part 2:

- 200 mg F06 coarse vs 200 mg F06 fine

If the number of subjects with reliable estimates of AUC_{0-inf} for any period falls below the planned number of evaluable subjects, then consideration will be given as to whether formal statistical analysis will be performed.

The adjusted means including differences from the pairwise comparisons listed above and their associated 90% CIs obtained from the model will be back transformed on the log scale to obtain adjusted GMRs and 90% CIs of the ratios, where the ratio, defined as

test/reference, will be presented. In addition, these will be presented together with the p-value from the pairwise treatment comparison and the intra-subject variability values (denoted as CVw in the results table), where the null hypothesis is defined as no treatment difference.

The intra-subject variability values will be calculated for all treatments combined and are obtained from the residual term from the SAS Software output. These values are calculated as follows:

$$CVw = 100 \times [\exp(\text{Mean Square Error}) - 1]^{1/2}$$

The ANOVA table from the model with F-statistic and p-value for the fixed effects will be presented on a separate page.

The statistical analysis will be performed using actual treatment received and planned sequence as detailed on the randomization schedule. The model will be fitted using the SAS Software procedure PROC MIXED, the method will be specified as Restricted Maximum Likelihood and the denominator degrees of freedom for the fixed effects will be calculated using Kenward and Roger's method [1]. The following is an example of the SAS Software code that will be used:

```

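### Do the replacement rules conflict over subjects withdrawn for drug-related adverse events, and does that put the primary AUC0-inf analysis at risk?

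*Protocol*

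**What the plan says.** **Replacement.** Protocol 4.6.1, repeated in 4.6.2, says that a subject who leaves early because of an "IMP-related adverse event or termination of the study will be considered to have completed the study, and will not be replaced". The next sentence gives the general position, part by part: "Subjects who discontinue study treatment may be replaced at the discretion of the Sponsor and the investigator to ensure a minimum of 12 evaluable subjects". Protocol 4.1 sets the ceiling: "Up to 4 replacement subjects per study part are permitted in this study to ensure sufficient evaluable subjects", so at most 19 are dosed in Part 1 and 20 in Part 2. Protocol 6.1 (also the synopsis) repeats the permission, the aim being 12 per part who finish with evaluable PK data from every period: "Subjects who withdraw from the study may be replaced at the discretion of the Sponsor and investigator to ensure that in each part 12 subjects". SAP 5.2 carries the same sentence. SAP 3.2.1 says of evaluability: "This will be monitored during the clinical phase to identify any requirement for replacement subjects". The exception in 4.6 does not appear in the SAP.

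**Analysis.** AUC0-inf and Cmax of entrectinib and M5 are the primary parameters (Protocol 6.5). Under SAP 9.2, estimates that rest on a terminal fit with R-squared below 0.9, or on more than 20% extrapolation, "will be deemed unreliable and will be listed but excluded from the summary statistics and formal statistical analysis". SAP 9.2.4 adds that if the number of subjects with reliable AUC0-inf in any period "falls below the planned number of evaluable subjects, then consideration will be given as to whether formal statistical analysis will be performed". The planned number, from SAP 5.2, is 12.

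**The concern.** Two things look wrong. First, one section forbids replacing a class of subjects, while three others allow replacement without naming an exception, and two of those (Protocol 6.1 and SAP 5.2) say its purpose is to secure 12. A site following 4.6 and a statistician following SAP 5.2 could expect different numbers.

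Second, the 12 returns as a trigger in the analysis. If drug-related withdrawals cannot be replaced, they use up the spare subjects, and below 12 the primary AUC0-inf comparison becomes a case-by-case decision. SAP 9.2.4 gives no criterion, and the decision would be made in an open-label study with the PK results available. If the concern held, a primary comparison could be run or dropped after the data were seen, and the replacement rule would affect how often that happened.

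**Working it through.** **1. Can all the replacement sentences be obeyed together?** Section 4.6 states a prohibition for one class (drug-related adverse event, or study termination). The sentence after it, Protocol 6.1 and SAP 5.2 state a permission, exercised at discretion, for withdrawals generally; 4.1 caps it at 4. None of them requires that a drug-related withdrawal be replaced. A sponsor who replaces other withdrawals and leaves this class unreplaced breaks none of them. Nor does counting such a subject as a completer hide a shortfall, because 6.1 asks for 12 who complete and also have evaluable PK data from all periods.

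**2. The plan's own precision figure.** Inputs from Protocol 6.1: CV 20%, n = 12, 90% CI.

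- s_w = sqrt(ln(1 + 0.20²)) = 0.198
- Fold-width = exp(t(0.95, df) × s_w × sqrt(2/n)), with df = 2n − 4 in Part 1 (three periods) and n − 2 in Part 2
- Part 1, n = 12: exp(1.725 × 0.198 × 0.408) = 1.150
- Part 2, n = 12: exp(1.812 × 0.198 × 0.408) = 1.158

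Both are inside 1.25x, so the stated figure is confirmed. Going lower:

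| n | Part 1 | Part 2 |
|---|---|---|
| 11 | 1.158 | 1.167 |
| 7 | 1.212 | 1.238 |
| 6 | 1.237 | 1.276 |
| 5 | 1.276 | 1.343 |

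These are expected widths. The 1.25x target is kept down to n = 6 in Part 1 and n = 7 in Part 2.

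**3. How likely is a fall below 12?** The spare subjects number 15 − 12 = 3 and 16 − 12 = 4. Without replacement, falling below 12 needs at least 4 of 15 or 5 of 16 lost. With all 4 replacements it needs at least 8 of 19 or 9 of 20. The documents give no withdrawal rate, so p is assumed:

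| p | Part 1: P(Bin(15,p) ≥ 4) | Part 1: P(Bin(19,p) ≥ 8) | Part 2: P(Bin(16,p) ≥ 5) | Part 2: P(Bin(20,p) ≥ 9) |
|---|---|---|---|---|
| 5% | 0.5% | <0.1% | 0.1% | <0.1% |
| 10% | 5.6% | <0.1% | 1.7% | <0.1% |
| 20% | 35.2% | 2.3% | 20.2% | 1.0% |

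The 20% row is hard to reach. Protocol 4.6.1 halts the study after one serious related reaction, or two severe related ones in the same cohort, so 4 or 5 drug-related withdrawals would have to build up with no serious reaction and, taking a cohort to be a study part, at most one severe one. Protocol 1.1.2.1 reports no serious adverse events in 323 healthy subjects given single doses and calls those doses generally well tolerated.

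**4. Does the SAP 9.2.4 trigger depend on the replacement rule?** Only in part. It counts reliable AUC0-inf values per period, so fit or extrapolation flags can set it off with nobody withdrawn. In Part 1 at p = 5% without replacement, one flagged value in the same period raises the chance to P(Bin(15, 0.05) ≥ 3) = 3.6%, and two raise it to P(Bin(15, 0.05) ≥ 2) = 17.1%. That rise comes from the flags.

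For entrectinib, extrapolation flags should be uncommon. With the stated half-life of 20 to 30 h, sampling to 96 h and a simple mono-exponential decline, the extrapolated share is about 2^(−96/20) = 3.6% to 2^(−96/30) = 10.9%, below the 20% cut-off. No half-life is given for M5, so the same cannot be said there.

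**The case for a change.** The strongest case for a change is that nothing in the protocol labels 4.6 as an exception, and that if it is one, the stated purpose of securing 12 is not guaranteed for this class. That is true as far as it goes. But the purpose is already limited by the sponsor's discretion and by the cap of 4, so it was never a guarantee. A cross-reference to 4.6 would be tidier, but it would alter no result.

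The second argument carries more weight: SAP 9.2.4 names no criterion for deciding whether a primary comparison is run, and reliability is known only after the parameters have been derived. SAP 3.2.1 also says that the evaluability definition is not used in reporting, yet 9.2.4 borrows the planned evaluable number. This stands as a gap in wording. The precision results even weaken the case for the discretion, since the model is still informative well below 12. The same fact shows what a sensible analyst would do: fit the specified mixed model to the reliable values. The results table shell in the SAP (Table 14.2.1.3.1) already shows n for test and reference beside the ratio and 90% CI. If the model were not fitted, AUC0-inf would still be listed and summarised, and the Cmax and AUC0-t comparisons do not carry this trigger.

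A further suggestion, to state in SAP 7.2 that these subjects are tabulated as discontinued, adds little. SAP 7.2 already presents discontinuations by reason, and Protocol 4.6.2 requires the reason on the eCRF.

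**Conclusion.** No change is needed. The replacement sentences fit together as a discretionary permission with one excluded class; what is missing is a cross-reference, which is editorial. The open wording in SAP 9.2.4 is a separate lack of detail that the planned model and table layout fill.

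The practical size is small. At an assumed 5% drug-related withdrawal rate, the chance of falling below 12 without replacement is 0.5% in Part 1 and 0.1% in Part 2. Losing one subject below 12 widens the expected CI bounds from 1.150x to 1.158x (Part 1) and from 1.158x to 1.167x (Part 2), against a target of 1.25x. The objective is exploratory and no stated figure is wrong.

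This rests on the protocol's CV of 20%, on a withdrawal rate nearer 5% than 20% (plausible from the reported tolerability, but not given in the documents), and on reliability flags being uncommon. The last is supported for entrectinib by its stated half-life and cannot be checked for M5.
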